Upper gastrointestinal endoscopies are commonly performed in patients planned to undergo bariatric surgery in order to detect and possibly treat lesions that could otherwise affect the surgery to be performed. Also, it can identify lesions that may complicate surgery or produce additional symptoms in the post-operative period. Obese patients present a challenge to the anesthesiologist due to their propensity for airway obstruction when exposed to agents commonly used for upper endoscopies including propofol, midazolam, and fentanyl. The increased incidence of obstructive sleep apnea (OSA) in this population further puts these patients at risk for obstruction in the peri-operative and post-operative period. Ketamine is an agent that has a possibility to provide some benefit to this population through its ability to maintain spontaneous airway reflexes and have less of an effect on spontaneous ventilation as the aforementioned agents. Through the combination of ketamine with propofol we hope to decrease the incidence of airway obstruction in this population while still maintain an adequate depth of anesthesia to allow the gastroenterologist to carry out the upper endoscopy efficiently.

1) Objectives

Research Question: Can ketamine combined with propofol create an adequate depth of anesthesia for an upper gastrointestinal endoscopy while decreasing the incidence of airway obstruction?

The frequency of bariatric surgery is increasing, and the incidence of comorbidities, such as obstructive sleep apnea are being recognized more and more often in this patient population. This produces challenges for managing these patients safely in the perioperative and post-operative period. We hope to establish that a ketamine and propofol combination can produce adequate procedural conditions while decreasing the incidence of airway obstruction without a significant increase in time to discharge compared to the use of propofol as a sole agent.

Mount Sinai

T 137	
Protocol Name:	Ketamine and Propofol Combination versus Propofol for Upper
	Gastrointestinal Endoscopy
Principal Investigator:	[name]
Primary Contact	[name]
Name/Contact Info:	[contact]; [contact]
Date Revised:	08/28/2015
Study Number:	IF#: 1790780

2) Background

Provide the scientific or scholarly background for, rationale for, and significance of the Human Research based on the existing literature.

Literature was reviewed regarding the use of ketamine for procedural sedation in the bronchoscopy and endoscopy suite as well as sedation for emergency department procedures. The combination of ketamine with other anesthetic agents has been shown to result in decreased dosage requirements of other agents, decreased incidence of airway obstruction requiring assistance, and mixed results regarding recovery time with some studies demonstrating quicker recovery including in obese patients and others demonstrating unchanged or prolonged recovery times with higher doses (2mg/kg) of ketamine. A large portion of the literature focuses on the use of ketamine in procedural sedation for emergency department (ED) procedures, especially in the pediatric population. Studies involving adults and endoscopy/bronchoscopy demonstrate overall positive results, however there is a dearth of literature involving the use of ketamine in the obese population.

The benefits of ketamine compared to most other anesthetic agents lie in its ability to produce hypnosis and analgesia with minimal respiratory depression and in some cases stimulatory effects on respiratory drive. The population that would stand to benefit most from these attributes of the medication are those prone to airway obstruction such as overweight individuals. This is especially salient given the fact that individuals with a higher BMI may require higher doses of propofol, which causes significant respiratory depression and increased incidences of airway obstruction.

As more patients turn to bariatric surgery as a method of weight loss when conservative measures fail, there is an increased need for upper endoscopies on this population prior to the surgery. High BMI patients present a unique challenge to the anesthesiologist due to an unfortunate coupling of increased medication dosage and a higher risk of airway obstruction and desaturation due to changes in body habitus. As mentioned previously, the benefits of ketamine could significantly benefit this population due not only to the attributes of this medication but its ability to decrease the overall propofol dosage required to tolerate upper endoscopy.

Prior experiences in upper endoscopy in the bariatric population often involves the avoidance of adjuncts such as midazolam or fentanyl that can perpetuate the incidence of airway obstruction in the peri-operative and post-operative period in addition to causing delay in discharge from the PACU. These procedures result in higher dosing of propofol with increased incidence of hypotension along with increased incidence of apnea. Ketamine has been used on occasion to assist with anesthetic depth without increasing incidence of airway obstruction and respiratory depression, but the use is not regular

Protocol Name:	Ketamine and Propofol Combination versus Propofol for Upper
	Gastrointestinal Endoscopy
Principal Investigator:	[name]
Primary Contact	[name]
Name/Contact Info:	[contact]; [contact]
Date Revised:	08/28/2015
Study Number:	IF#: 1790780

enough to truly evaluate any benefit or harm that is modulated by the addition of ketamine to the anesthetic.

There is no preliminary data.

As the prevalence of obesity continues to increase in the United States, so does the incidence of comorbidities such as gastroesophageal reflux, hiatal hernia, and the occurrence of bariatric surgery. All of these situations often result in patients undergoing an upper endoscopy for diagnostic or therapeutic purposes. Selecting patients who are planned to undergo bariatric surgery will result in a snapshot of the high BMI population. Evaluating an induction technique that has the potential to provide protection of airway reflexes while providing adequate depth for endoscopy has the potential to provide additional information regarding an anesthetic technique that may be especially safe and beneficial to this patient population.

Few anesthetic drugs are able to provide hypnotic and analgesic effects without significant depression of airway reflexes or spontaneous breathing. Ketamine is one of these rare agents and its use in the obese patient population, who are already more prone to airway obstruction and respiratory depression, could result in evidence for a safer anesthetic technique.

References:

Tandon, M., et al. Addition of sub-anesthetic dose of ketamine reduces gag reflex during propofol based sedation for upper gastrointestinal endoscopy: a prospective randomised double-blind study. Indian Journal of Anaesthesia (58). July 2014.

The four clinicians involved in patient selection, protocol creation, and carrying out the study are all in constant communication throughout the process. The endoscopy center performs these procedures on a daily basis, many of whom would be candidates for our study. We aim to recruit 100 patients, and predict we can reach this goal within 6 months based on prior schedules.

5) Study Design

a) Recruitment Methods

Primarily recruitment of subjects will be through [name] practice involving patients receive an upper endoscopy prior to bariatric surgery.

Recruitment materials will primarily consist of a verbal explanation of the procedure to be performed, how it is normally carried out from the anesthetic perspective, and our primarily goal of adding ketamine to the induction agent.

b) Inclusion and Exclusion Criteria

Eligible patient population will consist of [name] patient population who are undergoing an upper GI endoscopy prior to consideration for bariatric surgery.

Protocol Name:	Ketamine and Propofol Combination versus Propofol for Upper
	Gastrointestinal Endoscopy
Principal Investigator:	[name]
Primary Contact	[name]
Name/Contact Info:	[contact]; [contact]
Date Revised:	08/28/2015
Study Number:	IF#: 1790780

Exclusion criteria consist of: History of schizophrenia/schizoaffective disorder/bipolar disorder/dementia, glaucoma, craniofacial abnormalities, epilepsy, allergy to study drugs (propofol or ketamine), or history of current intracranial mass lesion.

c) Number of Subjects

A preliminary power analysis predicted we need 30 patients per group (total 90) to have significance using a Wilcox Rank Sum Test assuming skewed data. We therefore intend to enroll 100 patients to account or potential subjects who may not be appropriate for inclusion in statistical analysis after data collection.

d) Study Timelines

Each individual subject will be followed until discharge from the PACU when the patient has made both the clinical endpoints as well as standard discharge criteria. We anticipate to enroll all patients within one year. We estimate that the study will be completed six months after the enrollment of all subjects.

e) Endpoints

Primary endpoint is the incidence of gagging on endoscope insertion.

Secondary endpoints consist of: mean arterial pressure and heart rate during procedure, dosage required to achieve conditions necessary to proceed with upper endoscopy, total dosage of medication used, incidence of peri-procedure or post-operative nausea and vomiting, incidence of airway obstruction necessitating airway maneuvering (chin lift, jaw thrust, etc.), incidence of emergence delirium, and time required until eligible for discharge from endoscopy post-anesthesia care unit (PACU).

Since repeat ketamine doses will not be administered there are no specific primary or secondary endpoint parameters that would result in an end of study. In the event that unsafe vital signs changes or reaction to endoscopy occurred, the procedure would be aborted as would be standard protocol at our institution.

f) Procedures Involved in the Human Research

The study design is a prospective clinical study regarding the use of a 1:2 Ketamine: Propofol mixture (50mg Ketamine to 100mg Propofol) for induction in the study arm compared to a sole 100mg Propofol induction technique. Following this all follow up boluses will consist of only propofol in both arms. Subjects will be evaluated for response to initial insertion of endoscope, need for follow up doses, changes in vital signs, incidence of airway obstruction, incidence of emergence delirium, and time to discharge from the PACU. No further follow up or evaluation is planned.

Protocol Name:	Ketamine and Propofol Combination versus Propofol for Upper
	Gastrointestinal Endoscopy
Principal Investigator:	[name]
Primary Contact	[name]
Name/Contact Info:	[contact]; [contact]
Date Revised:	08/28/2015
Study Number:	IF#: 1790780

The primary study protocol procedure is the administration of a ketamine vs. propofol and ketamine mixture with induction of anesthesia. The remainder of monitoring for safety and risk management are part of the normal anesthetic care all patients receiving upper endoscopy and evaluation prior to PACU discharge receive. Standard anesthetic monitors and vital sign monitoring will only differ in study patients in the use of a pre-determined 3-minute non-invasive blood pressure monitoring interval instead of the minimum 5-minute interval advised by the ASA.

Exclusion criteria is almost entirely based on comorbidities and conditions that have an association with an untoward reaction or intolerance to ketamine. In addition, the blood pressure monitoring intervals of 3 minutes are more frequent than the standard recommendation of 5 minutes, which allows providers to be more aware of any blood pressure changes as a result of the ketamine administration. In addition, upper endoscopy will not proceed until patient demonstrates an adequate Ramsay sedation scale score of >5 to reduce incidence of patient discomfort or recall.

Source records will include the patients chart for the specific endoscopy encounter in epic which will be used for demographic information and to monitor the patient's length of stay and any events that occurred in the endoscopy PACU. Compurecord will be used to collect data regarding medication administration, vital signs, and any intraoperative events including toleration of upper endoscopy and incidence of airway obstruction.

No data will be collected in the form of long-term follow up.

g) Specimen Banking

N/A

h) Data Management and Confidentiality

Data will be collected on paper that will indicate the patient's medical record and her study number assignment, and her initials. There will be no indication on these sheets of the patient's name. The data collection sheet is attached. The data on the sheets will be transferred to an Excel computerized spreadsheet without the patient's initials. The excel data base is in a computer with a password. Also, the excel program is protected by a password. Data will also be encrypted for confidentiality. We will have a separate binder that will have the patients name along with their medical record # should we need to recheck records for any reason. The binder with the data sheet will be kept in the co-investigator's office near the endoscopy suite that is kept locked at all times and can only be accessed through T-9 door code. The binder with the identifying information will be kept in the principal investigator's office, also a locked office via T9 code that is in a different building. Only the PI will have access to these records.

i) Provisions to Monitor the Data to Ensure the Safety of Subjects

There is no anticipation of more than minimal risk involved to subjects.

Mount Sinai

Protocol Name:	Ketamine and Propofol Combination versus Propofol for Upper
	Gastrointestinal Endoscopy
Principal Investigator:	[name]
Primary Contact	[name]
Name/Contact Info:	[contact]; [contact]
Date Revised:	08/28/2015
Study Number:	IF#: 1790780

j) Withdrawal of Subjects

The primary circumstance for which a subject would be withdrawn without their consent would result in vital signs on initial exam that are otherwise incompatible with proceeding with upper endoscopy, such as unexpected poor saturation on room air (SO2 <92%), vital signs and symptoms compatible with hypertensive urgency or emergency, or previously undiagnosed arrhythmia on EKG with associated clinical findings. Decisions based on these findings will vary with the anesthesia provider involved but could include withdrawal from study protocol and proceeding with upper endoscopy, or cancellation of upper endoscopy entirely with planned rescheduling once patient undergoes further workup.

6) Risks to Subjects

Reasonable risks include mild side effects from ketamine administration including hallucinations, dissociative sensation, or untoward sensory phenomenon, all of which can occur with propofol as well. This can result in prolonged PACU stay due to treatment. Studies in other areas using ketamine have shown a decreased incidence of these side effects when giving low doses such as ours for single administration.

7) Provisions for Research Related Harm/Injury

Every patient is followed intra and post operatively and assessed for complications and treated appropriately. The study patients will be treated the same in this regard.

8) Potential Benefits to Subjects

There is no expected long-term benefit from participation in the study.

9) Provisions to Protect the Privacy Interests of Subjects

No long-term follow up or post-operative phone contact beyond a normal post-operative check is planned for study participants. No personal information beyond what is required by a standard anesthesia pre-operative assessment will be collected and this information will be kept private by the same means it always is. Patient interviews will be conducted in individual private bays in the holding area as they always are unless otherwise indicated by the patient (wish to have partner present etc). Only patient initials will be used on the data collection sheet. This data will be stored in a locked cabinet and later on a password protected Mount Sinai computer. Only the PI will have access to the patient's identifiable information. Patients will be reassured that all their information will remain confidential and private.

10) Economic Impact on Subjects

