Ketamine and Propofol Combination Versus Propofol for Upper Gastrointestinal Endoscopy
Data Analysis Plan

PI: [name]

NCT02643979

Document Date: 12/20/2015

Ketamine and Propofol Combination Versus Propofol for Upper Gastrointestinal Endoscopy
NCT02643979
12/20/2015

Statistical Plan and Analysis:

All variables will be checked for normality via Shapiro Wilk Test. Our primary endpoint, since it is categorical in nature will be analyzed via chi square test. Each other categorical variable will be analyzed via chi square testing as well. For normally distributed variables, t-test will be used. For non-normally distributed variables non parametric tests such as Mann-Whitney-U and Wilcoxon Rank Sum will be used. Significance testing will all be two tailed, with a cutoff of 0.05 as the threshold for statistical significance.

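### The sample-size sentence contradicts itself (30 per group in two arms is 60, not 90) and is calculated for a rank-sum test, while the primary endpoint is gagging incidence tested by chi-square

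*Protocol*

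**What the plan says.** - **Size.** Protocol 5c reports a preliminary power analysis under which "we need 30 patients per group (total 90) to have significance using a Wilcox Rank Sum Test assuming skewed data". It then raises enrolment to 100 to allow for patients who cannot be analysed. Section 4 gives the same target of 100.
- **Arms.** Protocol 5f describes a ketamine-propofol mixture "for induction in the study arm compared to a sole 100mg Propofol induction technique", and adds that "all follow up boluses will consist of only propofol in both arms". Section 19 describes two kinds of study syringe. A later sentence in 5f names the comparison differently: "administration of a ketamine vs. propofol and ketamine mixture with induction of anesthesia".
- **Primary endpoint.** Protocol 5e: "Primary endpoint is the incidence of gagging on endoscope insertion".
- **Primary analysis.** SAP: "Our primary endpoint, since it is categorical in nature will be analyzed via chi square test". All tests are two-tailed at 0.05. The SAP has no sample-size section.
- **Inputs.** Section 2 of the protocol says there are no preliminary data. Neither document gives a gagging rate, an effect size, a standard deviation, a power, or the variable that the rank-sum calculation was for.

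**The concern.** One sentence carries the whole justification of the trial's size, and it has two faults.

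The per-group and total figures do not agree for a two-arm design, and the enrolment target appears to be built on the total. A reader cannot tell whether the requirement is 30, 45 or 50 per arm.

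The calculation is also for a rank-sum test on a skewed variable. That says nothing about the power of a chi-square test on a proportion, so none of the three candidate sizes was derived for the endpoint that decides the trial. Reaching 30 evaluable patients per arm would satisfy the stated per-group requirement, and a null result on gagging could then be presented as adequately powered when nobody had worked out the power.

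**Working it through.** **1. The plan's own figure.** Inputs: 30 per group, total 90 and enrolment 100 (5c); two arms (5f, section 19).

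- 2 × 30 = 60, which is 30 short of 90.
- 90 = 3 × 30 or 2 × 45.
- Dropout does not close the gap. Going from 60 to 90 needs a loss of 1 − 60/90 = 33%, and from 60 to 100 a loss of 1 − 60/100 = 40%. By contrast 90/0.9 = 100 exactly, so the target looks like 90 plus a 10% allowance. A 10% allowance on 60 gives 60/0.9 = 67.

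The total of 90 is therefore not reproduced. The 30 per group cannot be checked under any test, because its inputs are not given.

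**2. What 30 per group means for a rank-sum test.** Two-sided 0.05, 80% power, relative efficiency 0.955 against the t-test (normal data):

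shift = (1.96 + 0.842) × √(2/30) / √0.955 = 0.723 / 0.977 = 0.74 SD

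The noncentral t version gives about 0.75 SD. Neither converts into a difference in gagging incidence.

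**3. What each size means for the planned primary test.** The control rates below are assumptions, because the documents give none. For two proportions with n per arm, p̄ = (p1 + p2)/2 and an uncorrected chi-square:

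power = Φ{ [ (p1 − p2) − 1.96 √(2p̄(1 − p̄)/n) ] / √[ (p1(1 − p1) + p2(1 − p2))/n ] }

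Example, 50% to 25% with n = 30: p̄ = 0.375; √(2 × 0.375 × 0.625/30) = 0.125; √(0.4375/30) = 0.1208. Power = Φ[(0.25 − 0.245)/0.1208] = Φ(0.041) = 0.52.

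| Halving of gagging | 30 per arm | 45 per arm | 50 per arm |
|---|---|---|---|
| 30% to 15% | 28% | 40% | 43% |
| 40% to 20% | 39% | 55% | 59% |
| 50% to 25% | 52% | 69% | 74% |
| 60% to 30% | 65% | 83% | 87% |
| 70% to 35% | 79% | 93% | 95% |

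Exact enumeration of the two binomials agrees closely: 28/42/44% from 30%, 52/70/75% from 50% and 80/92/95% from 70%. The SAP does not say whether a continuity correction applies. With one, power for 50% to 25% falls to about 41/61/67%.

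**4. Smallest fall detectable with 80% power.** From 50%, gagging must fall to about 17%, 22% or 23% with 30, 45 or 50 per arm. From 30%, it must fall to about 8% with 45 per arm or 9% with 50.

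**5. Size needed for a halving from 50%.** n = (1.96 √0.46875 + 0.842 √0.4375)² / 0.25² = 57.7, so 58 per arm. This is more than any of the three candidate sizes.

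**The case against.** The strongest reply is that the documents do not show which figure is the slip. The per-group number may be wrong (45 was meant), or the sentence may survive from a three-group design. That is right. What is established is that 30 and 90 are incompatible in a two-arm trial, not that 60 was intended.

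Second, the trial plans to enrol 100, so 45 to 50 per arm is the realistic size, and 60 evaluable patients would mean losing 40. This also stands. If 30 per group really were the requirement, the fault would run the other way: 100 would be 40 more than 60. The sentence does not let a reader decide between the two.

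Third, power depends on the assumed control rate. With gagging at 60% or 70% under propofol alone, 45 to 50 per arm gives more than 80% power for a halving. So the finding is that power for the primary endpoint is unknown, not that it is shown to be inadequate.

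Fourth, the rank-sum calculation may have been meant for a continuous secondary endpoint such as dose or time to discharge eligibility. The text does not say so, and even then the primary endpoint would have no calculation. That gagging is recorded as yes or no is an inference from the words incidence and categorical, but a strong one.

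**Conclusion.** The point holds on both counts, and the sentence must be corrected. The per-group and total figures differ by 30 patients for the two arms described, and nothing elsewhere in the protocol or SAP reconciles them. The stated test is not the test of the primary endpoint, so the trial has no sample-size basis for its main comparison.

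The practical size depends on the control gagging rate, which must be assumed. For a halving at 45 to 50 evaluable per arm, exact power runs from about 42–44% at a 30% control rate, through 70–75% at 50%, to 92–95% at 70%. At 30 per arm the same cases give 28%, 52% and 80%. These figures assume 1:1 allocation, an uncorrected chi-square test and two-sided 0.05.

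The differing description of the comparison in 5f is a separate drafting inconsistency. It supports the need to settle the arms but does not change the arithmetic.

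**What to change.** Replace the sentence in 5c with a two-arm, two-proportion statement, and repeat it in the SAP. The sponsor should state and justify a control gagging rate, the difference worth detecting and the power, and derive the number from them. If the target of 100 is kept, wording of this kind would be accurate:

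> 100 patients will be enrolled, 50 per arm, with at least 45 evaluable per arm. With a two-sided chi-square test at 0.05 without continuity correction, this gives 80% power to detect a fall in gagging from an assumed 50% to about 22–23%, or from an assumed 30% to about 8–9%.

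The rates in that text are placeholders until the sponsor justifies them. The SAP should also say whether the continuity correction is used.

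Delete the rank-sum basis, or attach it to a named continuous secondary endpoint with its own effect size. Reconcile the two descriptions of the comparison in 5f so that the arms are named the same way throughout.

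At an enrolment of 100 the cost is protocol and SAP wording only. The price is candour: the stated detectable effect will look less favourable than 30 per group implies. If the difference judged worth detecting is smaller than 100 patients can support, the sponsor must either enrol more or state the limited power openly.
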